10.2 Informed consent procedures

Eligible patients may only be included in the study after providing written (witnessed, where required by law or regulation), HA/IEC-approved informed consent, or, if incapable of doing so, after such consent has been provided by a legally acceptable representative of the patient. In cases where the patient's representative gives consent, the patient should be informed about the study to the extent possible given his/her understanding. If the patient is capable of doing so, he/she should indicate assent by personally signing and dating the written informed consent document or a separate assent form. Informed consent must be obtained before conducting any study-specific procedures (i.e. all of the procedures described in the protocol). The process of obtaining informed consent should be documented in the patient source documents.

Novartis will provide to investigators in a separate document a proposed informed consent form that complies with the ICH GCP guideline and regulatory requirements and is

considered appropriate for this study. Any changes to the proposed consent form suggested by the investigator must be agreed to by Novartis before submission to the HA/IEC, and a copy of the approved version must be provided to the Novartis monitor after HA/IEC approval.

Women of child bearing potential should be informed that taking the study treatment may involve unknown risks to the fetus if pregnancy were to occur during the study and agree that in order to participate in the study they must adhere to the contraception requirement for the duration of the study. If there is any question that the patient will not reliably comply, they should not be entered in the study.

10.3 Responsibilities of the investigator and HA/IEC

The protocol and the proposed informed consent form must be reviewed and approved by a properly constituted Institutional Review Board/Independent Ethics Committee/Research Ethics Board (HA/IEC) before study start. A signed and dated statement that the protocol and informed consent have been approved by the HA/IEC must be given to Novartis before study initiation. Prior to study start, the investigator is required to sign a protocol signature page confirming his/her agreement to conduct the study in accordance with these documents and all of the instructions and procedures found in this protocol and to give access to all relevant data and records to Novartis monitors, auditors, Novartis Clinical Quality Assurance representatives, designated agents of Novartis, HA/IECs, and regulatory authorities as required. If an inspection of the clinical site is requested by a regulatory authority, the investigator must inform Novartis immediately that this request has been made.

10.4 Publication of study protocol and results

Novartis assures that the key design elements of this protocol will be posted in a publicly accessible database such as clinicaltrials.gov. In addition, upon study completion and finalization of the study report the results of this trial will be either submitted for publication and/or posted in a publicly accessible database of clinical trial results.

11 Protocol adherence

Investigators ascertain they will apply due diligence to avoid protocol deviations. Under no circumstances should the investigator contact Novartis or its agents, if any, monitoring the trial to request approval of a protocol deviation, as requests to approve deviations will not be granted.

This protocol defines the study objectives, the study procedures and the data to be collected on study participants. Under no circumstances should an investigator collect additional data or conduct any additional procedures for any research related purpose involving any investigational drugs.

If the investigator feels a protocol deviation would improve the conduct of the study this must be considered a protocol amendment, and unless such an amendment is agreed upon by Novartis and approved by the HA/IEC it cannot be implemented. All significant protocol deviations will be recorded and reported in the CSR.

11.1 Protocol Amendments

Any change or addition to the protocol can only be made in a written protocol amendment that must be approved by Novartis, Health Authorities where required, and the HA/IEC. Only amendments that are required for patient safety may be implemented prior to HA/IEC approval. Notwithstanding the need for approval of formal protocol amendments, the investigator is expected to take any immediate action required for the safety of any patient included in this study, even if this action represents a deviation from the protocol. In such cases, Novartis should be notified of this action and the HA/IEC at the study site should be informed within 10 working days or less, if required by local regulations.

12 References

References are available upon request

1 ABBREVIATIONS

DME	Diabetic Macular Edema
BCVA	Best Corrected Visual Acuity
ECG	Electrocardiogram
ETDRS	Early Treatment Diabetic Retinopathy Study
FFA	Fundus Fluorescein Angiography
OCT	Optical Coherence Tomography
SAE	Serious Adverse Event
CRT	Central Retinal Thickness
VFQ-25	Visual Function Questionnaire

2 BACKGROUND

The purpose of this statistical plan is to define the tables, lists, data summaries and graphs to be prepared and to determine the statistical methods to be used for the analysis of the results of the study titled, “Randomized, Open-Label, Non-Inferiority Study Comparing the Safety and Efficacy of Wait and Extend Regimen with the Approved Treatment Regimen of Lucentis (Ranibizumab) in Turkish Patients with Visual Impairment due to Diabetic Macular Edema”. This statistical analysis plan has been prepared in pursuant to and in line with ICH-GCP principles and protocol no. IMM – 11 – 0003.

3 OBJECTIVES OF THE STUDY

3.1. PRIMARY OBJECTIVE

The primary objective of this study is to demonstrate that the “wait and extend” regimen of ranibizumab is non-inferior to the posology described in the prescribing information regarding the mean change in BCVA from baseline at month 12 in Turkish patients with vision loss due to diabetic macular edema.

3.2. SECONDARY OBJECTIVES

- To compare the mean change in CRT from baseline at month 12 between the two groups using OCT
- To evaluate the number of injections required for a treatment period of 12 months with a “wait and extend” dosing regimen
- To evaluate the number of visits required for a treatment period of 12 months with a “wait and extend” dosing regimen
- To evaluate the number of patients with improvement in BCVA from baseline
- To evaluate the number of patients with improvement of 5 or more letters from baseline
- To evaluate the number of patients with improvement of 10 or more letters from baseline
- To evaluate the number of patients with improvement of 15 or more letters from baseline
- To evaluate the safety of intravitreal Lucentis (ranibizumab) injections in patients with DME
- To describe patient-reported change in functional ability in patients treated with Lucentis

4 STUDY DESIGN

Study Design for the Prescribing Information Regimen Arm

Phase	Screening		Main Treatment			
Visit	1	2	3	4	5	6 -14
Month	0		1	2	3	4 – 12
Day	–7 to –1	B	30	60	90	120 – 360

Study Design for the Wait and Extend Regimen Arm

Phase	Screening		Main Treatment			
Visit	1	2	3	4	5	Number of visits may vary by patient response
Month	0		1	2	3	4 – 12
Day	–7 to –1	B	30	60	90	120 – 360

This is a randomized, controlled, multicenter, 12-month study concerning Lucentis (ranibizumab). Patients who provide consents will enter a screening period and their eligibility for enrollment will be evaluated. Following the screening period and evaluation of patient eligibility, only one eye will be selected / treated as the study eye. Once eligibility is confirmed, patients will be randomized to one of the following treatment arms:

Arm 1: Prescribing information regimen arm: Treatment will be given monthly and maintained until maximum visual acuity is achieved (patient's visual acuity remaining stable for three consecutive monthly assessments performed during ranibizumab treatment). Thereafter, patients will be followed-up monthly for visual acuity.

Treatment will be reinitiated in case a loss in visual acuity due to DME is determined during follow-up. Thereafter, monthly injections are to be performed until stable visual acuity is achieved for three consecutive monthly assessments (refers to at least two injections). The period between two doses should not be shorter than 1 month.

Arm 2: Wait and extend regimen arm: Lucentis (ranibizumab) 0.5 mg will be injected at baseline, and at months 1 and 2. Following the three loading doses at baseline, patients will be invited for a follow-up visit one month later. Once visual acuity becomes stable and OCT demonstrates no evidence of edema, patients will no longer be given intravitreal injections and they will be invited to return 6 weeks later. The interval will be extended by 2 weeks for a maximum of 8 weeks for as long as the patient exhibits stable visual acuity, central retinal thickness and clinical findings. In the event of a negative change, the interval will be reduced back to 4 weeks.

5 ANALYZED POPULATIONS

The study population will include male and female patients (above 18 years of age) who were admitted with Type 1 or Type 2 diabetes mellitus (according to ADA or WHO guidelines) with HbA1c values not exceeding 12.0% at screening (Visit 1). Patients should be following a diet, exercise and/or pharmacologic therapy for diabetes mellitus and should have vision loss for focal or diffuse macular edema with central involvement in at least one eye as demonstrated by color fundus photography, fluorescein angiography and OCT over a period of 28 days prior to initial treatment. A total of 86 patients from 12 centers in Turkey are expected to be randomized. Because a screening failure rate of 20% is anticipated, 104 patients will be needed to be screened.

5.1. SAMPLE SIZE CALCULATION

A sample size of 86 patients (43 patients in each treatment arm) will provide 90% power to determine a non-inferiority margin of 5 letters between the treatment arms with a significance level of 0.025 for the test, and the mean (standard deviation) letter change of the prescribing information regimen arm will be approximately 7 (7). A 20% discontinuation rate is initially assumed in order to account for the missing data expected for a follow-up period of 1 year; thus, at least 104 patients (52 patients in each treatment arm) will be included in the study.

6 ANALYSIS PLAN

The number of attendance of the patients in each treatment group to visits and the total number of patients will be expressed as n and % in the table that should be available in the very beginning of the analysis.

6.1 DEMOGRAPHICS

- **Patients gender data:** Patients, male and female, in both treatment regimens will be expressed separately as n and %.
- **Patients age:** Patient age data for patients in the “Approved treatment regimen” and in the “Wait and extend treatment regimen” arms will be tabulated by calculating n, mean, standard deviation, minimum, maximum, median and 95% confidence interval. Patients will be grouped by age as 18-64 years, 65-84 years and ≥ 85 years, and patients in each age group will be listed as n and %.

6.2 STUDY EYE

Study eyes (Right Eye or Left Eye) of the patients randomized to either of the two treatment regimens will be listed as n and %.

6.3 MEDICAL HISTORY

Medical history before the written informed consent date and current medical conditions not related with the studied indication will be listed together with as n and % values.

6.4 VITAL FINDINGS

Patients’ height (cm) and weight (kg) measurements will be tabulated providing descriptive statistics (n, mean, standard deviation, minimum, median, maximum and 95% confidence interval). Body Mass Index will also be calculated from height and weight variables using the Height / (Weight)² formula, and will be described again using descriptive statistics.

Systolic and Diastolic Blood Pressure (mm/Hg) measurements taken in the sitting position will be listed together with descriptive statistics.

These evaluations will be performed for 14 visits for the patient group receiving the “Approved Treatment Regimen” and for all visits to which the patients attend for the group receiving the “Wait and Extend” treatment regimen.

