4.1 Inclusion criteria

Patients eligible for inclusion in this study have to fulfill **all** of the following criteria:

1. Written informed consent must be obtained before any assessment is performed.
2. Male or female patients >18 years of age who have signed an informed consent
3. Patients with Type 1 or Type 2 diabetes mellitus (according to ADA or WHO guidelines) with HbA1c not more than 12.0% at screening (Visit 1). Patients should be on diet, exercise, and/or pharmacological treatment for diabetes.
4. Patients with visual impairment due to focal or diffuse macular edema with center involvement in at least one eye, as demonstrated with color fundus photography, fluorescein angiography and OCT within 28 days of the baseline treatment. If both eyes are eligible, the one with the worse visual acuity, as assessed at Visit 1, will be selected for study treatment unless, based on medical reasons, the investigator deems the other eye the more appropriate candidate for study treatment. The study eye must fulfill the following criteria at Visit 1:
 - BCVA score between 78 and 39 letters, inclusively, using ETDRS-like visual acuity testing charts at a testing distance of 4 meters (approximate Snellen equivalent of 20/32 to 20/160)
 - Decrease in vision is due to DME and not due to other causes, in the opinion of the investigator

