6.5.2 Body Mass Index

Body Mass Index will be calculated using height in centimeters (cm) and body weight (to the nearest 0.1 kilogram [kg] in indoor clothing, but without shoes) and will only be measured only in Screening/Visit 1.

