9.2 Patient demographics and other baseline characteristics

Descriptive statistics for continuous variables (i.e.: N, mean, standard deviation, median, maximum and minimum) and frequency and percent ranges for categorical variables will be given. Demographic data of the patients (including height and weight) and baseline visual acuity will be submitted as summary tables. Medical history and ocular medical history will be summarized per treatment arms.

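### The SAP's BMI formula exchanges height and weight and states no conversion from cm to m, so every BMI value it yields is wrong

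*SAP*

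**What the plan says.** SAP section 6.4 starts from the recorded measurements: "height (cm) and weight (kg) measurements will be tabulated providing descriptive statistics". It then gives the derivation: "Body Mass Index will also be calculated from height and weight variables using the Height / (Weight". The formula continues with a closing bracket and a superscript 2, so it reads height divided by weight squared. BMI is to be summarised with the same descriptive statistics as height and weight: n, mean, standard deviation, minimum, median, maximum and 95% confidence interval.

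Protocol section 6.5.2 lists the ingredients without a formula: "Body Mass Index will be calculated using height in centimeters (cm) and body weight (to the nearest 0.1 kilogram". It limits the measurement to one occasion: it "will only be measured only in Screening/Visit 1". Protocol section 9.2 is the general rule for baseline tables: "Demographic data of the patients (including height and weight) and baseline visual acuity will be submitted as summary tables". It does not name BMI.

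**The concern.** BMI is defined as weight in kg over height in metres squared. The SAP puts height in the numerator and squares weight. It also works from height in cm without saying that it must be converted.

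This is an instruction, not background text. The SAP states in its section 2 that it exists to define the tables and the methods, and section 6.4 tells the programmer how to derive the variable. If the line is followed, the BMI summary in both arms means nothing. If a programmer quietly corrects it, the output departs from the plan with no record of the change.

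BMI is a natural baseline descriptor in a trial restricted to patients with diabetes, and readers will look at it to judge the population and the balance between arms.

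**Working it through.** **Inputs.** Height in cm and weight in kg, and the formula, come from SAP 6.4. Protocol 6.5.2 gives the same inputs, with weight to the nearest 0.1 kg. The population is adult (Protocol 4.1: "Male or female patients >18 years of age who have signed an informed consent"). The documents report no BMI value, so there is no figure of the plan's own to reproduce. The patients below are illustrative and assumed.

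**Step 1: the two formulas side by side.** Let h be height in cm, m = h/100 and w weight in kg. The SAP quantity is h / w². BMI is w / m².

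| Height (cm) | Weight (kg) | SAP rule, h / w² | BMI, w / m² |
|---|---|---|---|
| 150 | 50 | 150/2500 = 0.060 | 50/2.25 = 22.2 |
| 160 | 70 | 160/4900 = 0.033 | 70/2.56 = 27.3 |
| 170 | 80 | 170/6400 = 0.027 | 80/2.89 = 27.7 |
| 180 | 90 | 180/8100 = 0.022 | 90/3.24 = 27.8 |
| 190 | 120 | 190/14400 = 0.013 | 120/3.61 = 33.2 |

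The SAP column falls as BMI rises.

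**Step 2: could the rule be right for anyone?** Setting 100m / w² = w / m² gives w³ = 100m³, so w = 4.64m. That is 6.5 kg at 140 cm, 7.9 kg at 170 cm and 9.3 kg at 200 cm. If height were entered in metres, equality needs w = m, that is 1.4 to 2.0 kg. Neither is possible for an adult. Over an assumed grid of 140 to 205 cm and 35 to 200 kg, the SAP rule gives 0.0035 to 0.167, while BMI runs from 8.3 to 102. The ratio of the two is 100m³ / w³, largest at 205 cm and 35 kg: 100 × 8.615 / 42875 = 0.020. The SAP value is therefore never more than about 2% of the true one.

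**Step 3: is it only a scale error?** No. Writing B for BMI and substituting w = B × m² gives h / w² = 100 / (B² × m³). Check at 170 cm, 80 kg: 100 / (27.68² × 4.913) = 0.027, as in the table. At a given height the SAP quantity varies as one over BMI squared, so it reverses the order of patients. It also depends on height, so no single multiplier recovers BMI.

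In an assumed population (BMI mean 30, SD 5; height mean 165 cm, SD 9) the simulated rank correlation with true BMI is -0.89. Varying the assumed SDs (BMI 3 to 7, height 6 to 12 cm) moves it between -0.66 and -0.97. The sign is stable; the exact figure depends on the assumptions.

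**Step 4: is swapping the terms enough?** No. Without converting cm to m, 170 cm and 80 kg gives 80/170² = 0.0028. The conversion has to be written in as well.

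**The case against.** The strongest reply concerns weight, not correctness. BMI decides nothing in this trial. It is absent from the eligibility criteria, the primary and secondary variables, the sample size calculation and the SAP's efficacy tests. No analysis adjusts for it, splits by it or ranks by it, so the reversal of order distorts no inference. Values near 0.03 would probably be noticed on the first output. Height and weight are tabulated in the same section, so BMI can be recomputed at any time. The line is most naturally read as two words transposed in drafting. All of this stands, and it limits the consequence.

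On wording, the SAP formula states no units of its own. The length-unit fault is that height is recorded in cm and no conversion is given. Protocol 6.5.2 is not itself in error, since it only says which measurements are used; it is cited because it does not correct the SAP.

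What does not stand is that the point can be left alone. The printed formula is intact, with the square plainly on weight, so this is not an extraction fault. No other text supplies the right rule. Relying on a programmer to notice means relying on an undocumented departure from the plan.

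**Conclusion.** The SAP's BMI derivation is wrong as written. Followed literally, it gives a wrong value for every patient in both arms: about 0.03 where BMI is about 27 to 28 for the 160 and 170 cm patients in the table, with heavier patients scoring lower. This rests on the standard definition of BMI and on the units that the SAP itself states. The only assumed inputs are the illustrative heights and weights, and the conclusion holds across the whole adult range.

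The effect is limited to one descriptive summary. No efficacy or safety conclusion depends on it, and the raw data are sound. It should be corrected, but it does not rank with problems in the primary analysis.

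**What to change.** In SAP section 6.4, replace the formula with: BMI (kg/m²) = weight (kg) / [height (cm) / 100]². This corrects both the exchange of terms and the missing conversion. For 170 cm and 80 kg it returns 80/1.70² = 27.7.

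In the same edit, say that BMI is summarised at Screening/Visit 1 only, as in Protocol 6.5.2. The closing paragraph of SAP 6.4 applies the section's evaluations to all visits and could be read as including BMI.

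The cost is one or two lines of SAP text. Data collection, the CRF, sample size and trial conduct do not change.

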9.5.2 Safety variables

All safety evaluations will be summarized and submitted for each visit per treatment arm.

All adverse events will be summarized per treatment arm, as patient numbers and per cents for any adverse event experience and adverse events for each system organ class will be summarized. All information collected (i.e.: severity or grade or causality assessment) will be summarized. Deaths and SAEs requiring early discontinuation will be summarized separately.

Laboratory details will be submitted as the descriptive statistics of the core data and for changes in the baseline data for each treatment arm (mean, median, standard deviation, interval) will be analyzed by highlighting the clinically notable changes.

Vital signs will be summarized and descriptive statistics will be given for heart rate and pulse in a sitting posture including the baseline changes.

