6.5 LABORATORY TESTS

Patients' HbA1C and Fasting Blood Glucose values will be listed for 14 visits for the patient group receiving the "Approved Treatment Regimen" and for all visits to which the patients attend for the group receiving the "Wait and Extend" treatment regimen, together with the descriptive statistics (n, mean, standard deviation, minimum, median, maximum and 95% confidence interval).

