6.9 BCVA (BEST CORRECTED VISUAL ACUITY) – FROM 4 METERS WITH ETDRS

Descriptive statistics (n, mean, standard deviation, minimum, median, maximum and 95% confidence interval) for BCVA Test scores applied to both eyes will be tabulated for all 14 visits for the patient group receiving the “Approved Treatment Regimen” and until the last available visit for the patient group receiving the “Wait and Extend” treatment regimen. For both treatment groups, the change between the first and final visits will be compared using the t-test for paired sequences or Wilcoxon Signed Rank Test based on the fit of the data to normal distribution.

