6.10 INTRAOCULAR PRESSURE (IOP) EXAMINATIONS

Descriptive statistics (n, mean, standard deviation, minimum, median, maximum and 95% confidence interval) for Intraocular Pressure values will be collected for all 14 visits for the patient group receiving the “Approved Treatment Regimen” and until the last available visit for the patient group receiving the “Wait and Extend” treatment regimen.

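### From Visit 6 the SAP's by-visit tables put the two arms on different time scales, and the late wait-and-extend rows are selected on response

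*SAP*

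**What the plan says.** For vital signs, SAP 6.4 states: "These evaluations will be performed for 14 visits for the patient group receiving the" approved regimen, and "for all visits to which the patients attend for the group receiving the" wait-and-extend regimen. SAP 6.5 has the same split for HbA1c and fasting glucose, which "will be listed for 14 visits for the patient group receiving the" approved regimen and for all attended visits in the other arm.

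Under SAP 6.9, "BCVA Test scores applied to both eyes will be tabulated for all 14 visits for the patient group receiving the" approved regimen. In the wait-and-extend arm the BCVA table runs to the last visit available. SAP 6.10 treats IOP likewise, "until the last available visit for the patient group receiving the" wait-and-extend regimen. The eye-examination tables in SAP 6.8.1 follow the same pattern.

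Protocol 9.5.2 adds: "All safety evaluations will be summarized and submitted for each visit per treatment arm".

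The schedule explains why this matters. The design table in SAP 4 gives both arms the same days up to Visit 5 (day 90). After that the labelled arm is monthly, and for the wait-and-extend arm the table says "Number of visits may vary by patient response". A stable patient without edema gets no injection: "they will be invited to return 6 weeks later". The interval then grows to at most 8 weeks and returns to 4 weeks after a negative change.

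Neither document gives an analysis window for these tables or a rule assigning wait-and-extend visits to months.

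**The concern.** The trial compares two visit schedules, so visit number is not a common time axis. After Visit 5 it marks a fixed month in one arm and a response-dependent date in the other. A reader who sets the two columns side by side would be comparing different lengths of follow-up.

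There is also selection. The wait-and-extend interval depends on visual acuity, retinal thickness and clinical findings, so the number of visits a patient accumulates depends on response. High visit numbers drop the patients who stayed stable. A wait-and-extend BCVA mean at Visit 12 is therefore conditional on earlier non-stable assessments, and the labelled-arm mean at Visit 12 is not.

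At stake is the described 12-month course of BCVA, IOP, blood pressure, HbA1c and glucose. Without a rule set in advance, the time axis would be chosen during programming of an open-label trial.

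**Working it through.** **1. The plan's figure of 14 visits.** Screening (Visit 1) + baseline (Visit 2) + 12 monthly visits = 14. Labelled Visit k falls on day 30 × (k − 2), so Visit 14 is day 360. This agrees with Protocol 5.5.10 and the Protocol Section 6 schedule.

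**2. Wait-and-extend dates for a continuously stable patient.** Visit 5 is day 90. The next intervals are 42 days, then 56 days each.

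| Visit | Wait-and-extend, always stable | Labelled | Gap (days) |
|---|---|---|---|
| 6 | 90 + 42 = 132 | 120 | 12 |
| 7 | 132 + 56 = 188 | 150 | 38 |
| 8 | 188 + 56 = 244 | 180 | 64 |
| 9 | 244 + 56 = 300 | 210 | 90 |
| 10 | 300 + 56 = 356 | 240 | 116 |

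Day 356 is within 7 days of day 360, so Visit 10 is this patient's Month 12 visit. No assumption beyond the stated rule is needed.

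**3. Who reaches Visit 11.** I read the rule as 28 days after a non-stable assessment, then 42, then 56 days while stable. The documents do not say whether a closing visit is added when the interval would pass Month 12, so both cases are shown.

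- *With a closing visit at day 360.* One non-stable assessment is enough. If it occurs at Visit 5, the later days are 118, 160, 216, 272, 328 and 360, and day 360 is Visit 11. Enumerating all stable/non-stable sequences, the minimum number of non-stable assessments is 1 for Visit 11, 2 for Visit 12, 3 for Visit 13 and 6 for Visit 14 (7 if 4 weeks is read as 30 days).
- *Without a closing visit.* Visit 11 is six intervals after Visit 5. The shortest total with one non-stable assessment is, for example, 42 + 28 + 42 + 56 + 56 + 56 = 280, giving day 90 + 280 = 370, which is too late. Two are needed.

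In both cases a continuously stable patient is absent from Visit 11 onward on planned dates.

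**4. How many reach it.** The documents give no chance of stability, so p, taken as constant and independent across visits, is an assumption.

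- *With a closing visit.* The patient stops at Visit 10 only if stable at all five assessments, Visits 5 to 9. The share reaching Visit 11 is 1 − p⁵: 1 − 0.9⁵ = 41%; 1 − 0.7⁵ = 83%; 1 − 0.5⁵ = 97%. By enumeration, Visit 12 is reached by 9% to 84%.
- *Without one.* Weighting the 2⁶ = 64 sequences over Visits 5 to 10 and requiring Visit 11 by day 360 gives 11% (p = 0.9), 58% (0.7) and 89% (0.5).

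The mean day of Visit 10 runs from 338 (p = 0.9) to 279 (p = 0.5), against 240 in the labelled arm.

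**5. Would time windows work?** Take targets at Months 4, 6, 8, 10 and 12 (days 120, 180, 240, 300 and 360).

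- The always-stable visits lie 12, 8, 4, 0 and 4 days from target. All five fall within ±15 days but only three within ±7.
- The patient with one non-stable assessment at Visit 5 has days 160, 216 and 272, which are 20, 24 and 28 days from the Month 6, 8 and 10 targets. Day 328 is 28 days from the Month 10 target. A ±15-day window therefore misses this patient at all three months.
- Adjoining 60-day windows (±30 days) always contain a planned visit up to Month 10, because the longest interval is 56 days. The price is looser timing.

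**The case against.** The strongest reply is that these tables are descriptive and specified separately for each arm. No between-arm test by visit number appears. BCVA and CRT are compared between arms at Month 12 (SAP 6.14.1, 6.14.2), FFA findings are compared between the first and Month 12 visits (SAP 6.12), and renal tests use Visits 1 and 5 (SAP 6.6). The SAP never says in words that wait-and-extend rows are numbered visits, and the protocol schedule sets both arms over the same month and day rows. The affected numeric tables report n, and SAP 6 opens with an attendance table, so thinning at late visits would be visible.

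Most of this stands and limits the consequence. It does not supply a time axis: visit is the only one these sections offer. Showing n reveals that a row is thin, but not that it was selected on response.

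A reader might infer that late wait-and-extend rows contain only unstable or the worst-controlled patients. The rule does not support that. A patient at Visit 11 may be stable again that day, and under some assumed values most of the arm gets there. If the ±7-day visit tolerance accumulated at every visit, a continuously stable patient would have Visit 10 on day 321 and could reach Visit 11 as well.

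**Conclusion.** The point holds for the descriptive tables in SAP 6.4, 6.5, 6.9 and 6.10. The misalignment follows from the stated schedule: for a continuously stable patient it grows from 12 days at Visit 6 to 116 days at Visit 10. The direction of selection from Visit 11 onward also follows from the rule on planned dates. The size of the selected group does not: 11–89% or 41–97% reach Visit 11, depending on the closing-visit convention and on an assumed stability probability of 0.9 to 0.5. No single percentage should be quoted.

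A reader might also infer that the non-inferiority comparison is distorted. The documents do not support that, because the between-arm BCVA comparison is set at Month 12 and not at a visit number. The within-arm test in SAP 6.9, from first to final visit, is a separate matter: it does not tie the final visit to Month 12.

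The change is worth making because it is cheap and these tables carry the course of vision and safety measures over the year. It does not bear on the primary conclusion.

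**What to change.** In SAP 6.4, 6.5, 6.9 and 6.10:

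- Present both arms by time since baseline, keeping the shared visits up to Month 3 and using prespecified, non-overlapping windows after that.
- State a maximum distance from each target day. One example is ±15 days around even months, an assumption for the sponsor to set. Because that width misses some schedules with a non-stable assessment, and so could itself select on response, check coverage against the possible schedules first. ±30 days is the widest that does not overlap at two-month spacing; assign boundary days to one window.
- Use each reading in at most one window, take the reading nearest the target with a stated tie rule, carry nothing forward, and show n per window and arm.
- Keep the by-visit safety summaries required by Protocol 9.5.2, and state that arms are not to be compared by visit number after Visit 5.

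The cost is SAP wording and a derivation from recorded visit dates, with no new data and no change to the visit schedule. With ±15 days, the labelled-arm readings on days 150, 210, 270 and 330 fall outside the windowed display, but they stay in the by-visit tables.
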